3.2.6. Pharmacokinetic Measures and Endpoints

3.2.6.1. Pharmacokinetics (PK) Ancillary Study

PK samples of laquinimod and its metabolites will be collected from approximately 15 patients per each of the three continuing treatment groups (at selected sites at Month 1), for a total of approximately 45 patients. Additionally, PK samples were collected from 2 patients in the laquinimod 1.5 mg/day treatment group when the treatment was stopped; no further PK samples will be collected from the laquinimod 1.5 mg/day treatment group.

The time of the previous dose as well as deviations from the blood sampling times will be recorded in the appropriate eCRF. Patients performing the 24-hour PK profile will come to the clinic after an overnight fast (minimum of 8 hours) and will be given breakfast 4 hours after drug administration.

Samples will be collected at pre-dose, 15, 30 min and 1, 2, 3, 6 and 24 hours post dose.

Steady state pharmacokinetic parameters for laquinimod (AUC_{τ} , C_{\max} and C_{\min} , t_{\max}), will be calculated for each patient. Additional parameters for laquinimod and pharmacokinetic parameters for its metabolites may be calculated if data permit.

For patients participating in this ancillary study, the morning dose and the 24 hours dose administration (the day after) will take place at the clinic.

3.2.6.2. Population PK (PPK) Study

A single blood sample will be collected from all patients at Months 1, 3, 6 and 12 for evaluation of laquinimod and its metabolites.

Pharmacokinetics of laquinimod will be evaluated using a Population PK approach. The effect of covariates on the PK of laquinimod will be evaluated. Possible covariates will include demographic variables (e.g., age, gender, body weight and ethnicity), clinical variables (e.g. CAG repeat length), concomitant medications, blood and urine chemistry variables and markers of renal (creatinine clearance and serum creatinine) or hepatic function. Pharmacokinetic parameters for laquinimod metabolites may be calculated if data permit.

The date and time of the blood sample, as well as the date and time of the last study drug dose prior to the sample will be recorded on the eCRF.

The PPK model may also include any unscheduled pharmacokinetic samples collected to assist with further investigations of cardiovascular events or other clinical event of interest for safety (see Section 8.1).

3.2.7. Pharmacodynamic Measures and Endpoints

Biomarker assessment will include the following:

- Cytokines, Soluble protein (or any other soluble marker) levels will be determined at baseline, Months 6 and 12.
- Monocyte gene expression and/or protein profile will be explored at baseline and Month 12. This study will be performed only at selected sites in a subgroup of patients.
- PET scans and imaging analysis of microglial activation marker TSPO will be performed at baseline and Month 12. This study will be performed only in a subgroup of patients.
- MRI scans for MRS to explore the potential effect on metabolic changes in the putamen and frontal white matter will be done in a subgroup of patients at baseline and Month 12.

3.2.8. Pharmacogenomic Measures and Endpoints

Pharmacogenomic (PGx) assessment will include CAG repeats analysis in the huntingtin gene and might include other DNA variations and RNA expression patterns potentially associated with clinical treatment responses to laquinimod (e.g. clinical effect, pharmacokinetics, tolerability, and safety features or disease susceptibility and severity features). The final list of genes that might be investigated will be selected in a later stage before the analysis so as to allow updating with new scientific information. Genomic analysis could also include a sequencing of the whole genome if required.

The CAG repeat length in the huntingtin gene will be established by a central laboratory for all patients, as part of the screening process to determine eligibility for the study. This will be done also for patients where a historical CAG repeat length result is available. If during this screening process a CAG repeat length result that differs from the patient's historical result is obtained, the central laboratory results should be used for determining eligibility. The exact CAG repeat length will not be available to the sites, only to the Sponsor. The central laboratory report will only note if the patient is within the eligibility criteria range (36-49 inclusive) or not. This will be explicitly explained and noted in the ICF of the patient. In either case, the investigator should review the CAG repeat results with the patient at the baseline visit, or at an unscheduled visit if a baseline visit will not take place.

3.3. Randomization and Blinding

This is a randomized, double-blind, placebo-controlled study. Prior to 10 January 2016, eligible patients were randomly assigned to receive treatment with laquinimod at a dosage of 0.5, 1.0 or 1.5 mg qd or a matching placebo in a 1:1:1:1 ratio.

As of 10 January 2016, following a decision to discontinue treatment of the laquinimod 1.5 mg dose arm, future eligible patients will be randomized in a 1:1:1 ratio to receive laquinimod 0.5 mg/day or 1.0 mg/day or matching placebo for 52 weeks. No change was performed to the original randomization list except that the patient numbers assigned to laquinimod 1.5 mg/day were removed from the list by the interactive response technology (IRT) vendor.

All patients who discontinued the 1.5 mg/day dose have been unblinded. No attempts will be made to re-randomize patients whose 1.5 mg treatment was stopped to a lower dose of laquinimod. The remaining ongoing patients retained their originally randomized treatment assignments.

Patients and investigators will remain blinded to treatment assignment during the study.

The randomization code will be generated by the Clinical Supply Chain (CSC) department following specifications from the Biostatistics Department.

In addition, the sponsor's clinical personnel involved in the study will be blinded to the study drug identity until the database is locked for analysis and the treatment assignment revealed. However, in case a prioritized sample analysis is needed, bioanalytical personnel may not be blinded. A statistician not assigned to the study will be responsible for reviewing the randomization code, and the final randomization code will be maintained by the CSC department.

Patients will be randomly assigned to treatment through a qualified randomization service provider (e.g., IRT). This system is used to ensure a balance across treatment groups.

3.4. Study Drugs and Dosage

Patients will be randomized to receive laquinimod 0.5, 1.0, or 1.5 mg qd or matching placebo (prior to 10 January 2016), or randomly assigned to receive treatment with laquinimod at a dosage of 0.5 mg/day, 1.0 mg/day or placebo in a 1:1:1 ratio (from 10 January 2016). Every patient will take 3 capsules once daily, at the same time of the day, during the entire study period. Study drug will be administered as described in Section 3.4.1 and Section 3.4.2 below. The capsules will be taken orally and must be swallowed whole with a glass of water. The capsule should not be opened. Laquinimod can be taken with or without food.

3.4.1. Investigational Product and Dosage

Laquinimod will be provided as off-white, opaque, hard gelatin capsules. The capsules should be swallowed whole with water.

- Patients randomized to the laquinimod 1.5 mg qd treatment arm received 3 capsules of 0.5 mg laquinimod (Note: The treatment of this high dose arm was discontinued as of 10 January 2016).
- Patients randomized to the laquinimod 1.0 mg qd treatment arm will receive 2 capsules of 0.5 mg laquinimod and 1 capsule of matching placebo.

- Patients randomized to the laquinimod 0.5 mg qd treatment arm will receive 1 capsule of 0.5 mg laquinimod and 2 capsules of matching placebo.

A more detailed description of administration procedures is given in Section 5.1.

3.4.2. Other Study Drugs and Dosage - Placebo

Matching placebo for laquinimod capsules will be provided as off-white opaque, hard gelatin capsules. Patients randomized to the placebo treatment arm will receive 3 capsules of matching placebo capsules.

A more detailed description of administration procedures is given in Section 5.1.

3.5. Duration of Patient Participation

Subjects are expected to participate in this study for approximately 14 months, consisting of a screening period of 2 weeks up to 5 weeks, a double-blind treatment period of 12 months and a 1 month follow-up period.

3.6. Stopping Rules and Discontinuation Criteria

Safety stopping rules are detailed in [Appendix A](#) (Guidance on Safety Monitoring).

These include:

- Elevated liver enzymes (as detailed in [Appendix A](#))
- Pregnancy
- Need for concomitant treatment with moderate and strong CYP3A4 inhibitors
- Patients that are diagnosed with a malignant solid or liquid tumor while participating in the study
- Acute coronary syndrome, myocardial infarction or any major cardiovascular event

Female subjects will be reminded to continue using 2 methods of acceptable contraception throughout treatment duration, and up to 30 days from the date from the last dose of the study drug, and about the need to stop treatment immediately if pregnancy is suspected. During the conduct of the study, serious adverse events will be reviewed (see Section 7.1.5) as they are reported from the investigational center to identify safety concerns. The study may be terminated by the sponsor at any time.

A patient may discontinue participation in the study at any time for any reason (e.g., lack of efficacy, consent withdrawn, and adverse event). The investigator and/or sponsor can withdraw a patient from the study at any time for any reason (e.g., protocol violation or deviation as defined in Section 11.1.1, noncompliance, adverse event).

Liver Impairment

To avoid exposures to higher levels of laquinimod (see Section 1.3.2.1), a stopping rule related to liver impairment has been introduced. Patients who develop any chronic liver disease associated with hepatic function impairment while participating in the study should stop study medication.

Renal Impairment

To avoid exposures to higher levels of laquinimod (see Section 1.3.2.1), a stopping rule related to renal impairment has been introduced. Patients who develop chronic renal disease associated with moderate or severe functional impairment, defined as estimated creatinine clearance (CrCl) <60 mL/min/1.73 m², while participating in the study should stop study medication temporarily, and the assessment of estimated CrCl should be repeated. If the development of renal impairment is confirmed (estimated CrCl <60 mL/min/1.73 m²), the patient should stop study medication permanently.

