Home urine pregnancy test			Starting after Month1 (Visit 3), a urine β-hCG test will be performed at home in women of child-bearing potential every 28 (±2) days.							
Site call to patient for result inquiry			A telephone call will be scheduled to be performed within 72 hours of the urine test date to inquire about the results.							
C-SSRS (baseline screening version)	X									
C-SSRS (since last visit version)		X	X	X		X	X	X	X	
Randomization		X								
MRI scan ^q	X ⁿ	X ^r						X ^s		
Estimated creatinine clearance calculation ^t	X	X	X	X		X	X	X	X	X ⁱ
MRS scan ^k		X						X		
PET scan ^{k u v}		X ^p						X ^p		

TV5600-CNS-20007 (LEGATO-HD)	Pre-treatment	Baseline (Dosing)	Double-blind Treatment Period						Follow-Up	Unscheduled Visit
Visit Number	Visit 1	Visit 2	Visit 3	Visit 4	Visit 5	Visit 6	Visit 7	Visit 8 - Termination Visit ^a	Visit 9	-
Time (Weeks)	Screening	Baseline	Week 4	Week 13	Week 19	Week 26	Week 39	Week 52	Week 56	-
Time (Months)		Month 0	Month 1	Month 3		Month 6	Month 9	Month 12 (or ET)		
Visit Window	2 weeks up to 5 weeks		±3 days	±7 days	±7 days	±7 days	±7 days	±7 days	±5 days	
UHDRS-TMS	X ^w	X	X	X		X		X		
UHDRS-TFC	X ^w	X				X		X		
UHDRS-FA		X				X		X		
mPPT		X				X		X		
PBA-s ^x		X						X		
CIBIS ^x		X								
CIBIC-plus ^x						X		X		
HD-QoL ^y		X						X		
EQ-5D-5L ^z		X						X		
WLQ ^z		X						X		
Q-Motor Assessments	X	X	X	X		X		X		
HD-CAB ^{aa}	X ^{bb}	X	X ^{cc}	X ^{cc}		X		X		
CDR-SB ^x		X						X		
HADS		X						X		
PK (drug and metabolites concentration) sampling			X ^y	X		X		X		X ⁱ
24-hour PK profiling ^{dd} for drug and metabolites			X							
Review study compliance		X	X	X	X	X	X	X		X
Study Drug Dispensing		X	X	X		X	X			
Study Drug Collection and Reconciliation			X	X		X	X	X		X

TV5600-CNS-20007 (LEGATO-HD)	Pre-treatment	Baseline (Dosing)	Double-blind Treatment Period						Follow-Up	Unscheduled Visit
Visit Number	Visit 1	Visit 2	Visit 3	Visit 4	Visit 5	Visit 6	Visit 7	Visit 8 - Termination Visit ^a	Visit 9	-
Time (Weeks)	Screening	Baseline	Week 4	Week 13	Week 19	Week 26	Week 39	Week 52	Week 56	-
Time (Months)		Month 0	Month 1	Month 3		Month 6	Month 9	Month 12 (or ET)		
Visit Window	2 weeks up to 5 weeks		±3 days	±7 days	±7 days	±7 days	±7 days	±7 days	±5 days	
Concomitant Medication Inquiry		Concomitant medication will be monitored throughout the treatment and follow-up periods.								
Adverse events inquiry		Adverse events will be monitored throughout the treatment and follow-up periods.								

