ⁿ ECG will be performed in triplicate at baseline (approximately 10±5 minutes apart). All other visits will have a single ECG performed.

^o At the screening visit, only serum β-HCG test will be performed. For the baseline visit - urine pregnancy test (beta human chorionic gonadotropin [β-hCG]) result is required for women of child-bearing potential prior to randomization. The urine test should be conducted at the site to allow randomization. A serum β-HCG test should also be used to confirm the urine test; however, the randomization should be performed based on the results of the urine pregnancy test.

Clinical Study Protocol with Am 04

- ^p An additional urine β -HCG test will be performed at the PET facilities at Imperial College in London at the Baseline visit and at Visit 8 for women of child-bearing potential participating in the PET substudy. Its result will be available on site prior to any procedures involving ionizing radiation and will be considered accordingly.
- ^q If anxiolysis is required in order to perform the MRI scan, the scan should be performed at the end of the study visit day.
- ^r The baseline MRI can be performed at the screening visit, but no later than 7 days prior to baseline. If performed at the screening visit, as many screening assessments as possible should be conducted prior to the MRI scan in order to assess eligibility.
- ^s If a patient terminates within 3 months of the baseline visit, they will not undergo an Early Termination scan. If a patient terminates prior to Month 12, the Early termination scans should be performed as soon as possible, but not more than 7 days after discontinuation of study drug. Month 12 scans should be performed 7 days prior to the Termination Visit. The early termination MRI scan was not to be done for the patients in the discontinued 1.5 mg/day treatment arm .
- ^t Estimated creatinine clearance will be calculated at all in clinic study visits. Patients who develop chronic renal disease associated with moderate or severe functional impairment, defined as estimated creatinine clearance (CrCl) <60 mL/min/1.73 m², while participating in the study should stop study medication temporarily and the creatinine clearance assessment should be repeated. If the renal impairment is confirmed (estimated CrCl <60 mL/min/1.73 m²), the patient should stop study medication permanently.

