4.2. Patient Exclusion Criteria

Patients will be excluded from participating in this study if they meet any of the following criteria:

- a. Use of immunosuppressive agents, or cytotoxic agents, including cyclophosphamide and azathioprine within 12 months prior to screening
- b. Previous use of laquinimod
- c. Use of moderate/strong inhibitors of CYP3A4 within 2 weeks prior to randomization.
- d. Use of inducers of CYP3A4 within 2 weeks prior to randomization.
- e. Pregnant or breastfeeding.
- f. **[Revision 1]** Serum levels $\geq 2 \times \text{ULN}$ of either ALT or AST at screening.
- g. **[Revision 1]** Serum direct bilirubin which is $\geq 1.5 \times \text{ULN}$ at screening.
- h. **[Revision 2]** Estimated creatinine clearance < 60 mL/min at screening, calculated using the Cockcroft Gault equation:
 $(140 - \text{age}) \times \text{mass (kg)} \times [0.85 \text{ if female}] / 72 \times \text{serum creatinine (mg/dL)}$
- i. **[Revision 1]** Subjects with a clinically significant or unstable medical or surgical condition that may put the patient at risk when participating in the study or may influence the results of the study or affect the patient's ability to take part in the study, as determined by medical history, physical examinations, ECG, or laboratory tests. Such conditions may include:
 1. A major cardiovascular event (e.g. myocardial infarction, acute coronary syndrome, de-compensated congestive heart failure, pulmonary embolism, coronary revascularization, angina) that occurred prior to randomization.
 2. Significant cardiovascular risk factors (such as, but not limited to, uncontrolled hypertension, uncontrolled diabetes), per investigator discretion.
 3. Any acute pulmonary disorder
 4. A CNS disorder other than HD that may jeopardize the subject's participation in the study, including such disorders that are demonstrated on the baseline MRI (based on local read).
 5. A gastrointestinal disorder that may affect the absorption of study medication.
 6. Acute or chronic renal disease including acute kidney injury (AKI).
 7. Any form of acute or chronic liver disease.
 8. Known human immunodeficiency virus positive status. Patients will undergo an HIV test at screening per local requirements, if applicable.
 9. Any malignancies, excluding basal cell carcinoma, in the 5 years prior to randomization.

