7.7. Estimated Creatinine Clearance Calculation

Significant changes in laquinimod exposure, in particular in terms of unbound drug fraction, are predicted in patients with renal impairment (see Section 1.3.2.1). Consequently, estimated CrCl will be calculated at all visits to monitor chronic renal function in the study in order to identify patients with potentially impaired laquinimod clearance. Patients with a confirmed CrCl <60 mL/min/1.73 m² should stop study medication temporarily, and the CrCl assessment should be repeated. If the renal impairment is confirmed (estimated CrCl <60 mL/min/1.73 m²), the patient should stop study medication permanently (see Section 3.6).

Following recent findings connecting Gd-based contrast agents and nephrogenic systemic fibrosis, the estimated CrCl result should be available prior to the baseline MRI scan. Estimated CrCl calculation will be done in accordance with the central laboratory creatinine value measurement performed at the screening visit. The central laboratory will report calculated estimated CrCl; however, if the result is not available prior to the baseline MRI scan, estimated CrCl may be calculated using the Cockcroft-Gault equation (eg, available online CrCl calculator: <http://reference.medscape.com/calculator/creatinine-clearance-cockcroft-gault>).

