 - additional investigations and follow-up per the investigator's discretion or sponsor's request

Necessary medical procedures including repeat labs will be performed based on clinical needs determined by the treating physician's judgement.

9. Guidance on monitoring subjects with CPK increase

- In case of CPK results $>ULN$, troponin and creatine kinase MB isoenzyme (CK-MB) will be tested by the central laboratory.
- In case of CPK $>10\times ULN$, an unscheduled visit to assess urine myoglobin will be required. The following blood tests will be repeated at the unscheduled visit: CPK, blood urea nitrogen, creatinine, electrolytes including potassium, calcium, phosphate.

10. Acute Coronary Syndrome, Myocardial Infarction or Any Major Cardiovascular Event

Patients who experience acute coronary syndrome, myocardial infarction or any major cardiovascular event will permanently discontinue treatment with study medication. Patients will be asked to continue all scheduled visits for safety assessment.

11. Liver Impairment

Patients who develop liver disease associated with liver functional impairment while participating in the study should stop study medication.

12. Renal Impairment

Patients who develop chronic renal disease associated with moderate-severe functional impairment, defined as estimated CrCl <60 mL/min/1.73 m², while participating in the study should stop study medication temporarily until normalization of renal function or confirmation of renal impairment diagnosis. In case moderate-severe renal impairment is diagnosed, the patient will permanently discontinue treatment with study medication.

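### Renal entry limit is in mL/min but the stopping limit is in mL/min/1.73 m², with no conversion given; Section 7.7 also sets a different trigger for the temporary hold than Section 3.6

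*Protocol*

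**What the plan says.** **Entry.** Section 4.2, exclusion h (repeated in the synopsis), excludes on "Estimated creatinine clearance < 60 mL/min at screening, calculated using the Cockcroft Gault equation" and prints the formula. The limit is in mL/min.

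**Monitoring.** Table 3 has a single row, "Estimated creatinine clearance calculation", marked at screening, baseline, every later in-clinic visit and unscheduled visits. Section 7.7 says that the central laboratory reports the calculated value, without giving its equation or unit. If that report is late for the baseline MRI, "estimated CrCl may be calculated using the Cockcroft-Gault equation".

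**Stopping.** Section 3.6 applies to patients in whom chronic renal disease arises with moderate or severe functional impairment, "defined as estimated creatinine clearance (CrCl) <60 mL/min/1.73 m²". They are held, retested, and stopped for good if the low value is confirmed. Table 3 footnote t has the same condition and order: such patients "should stop study medication temporarily and the creatinine clearance assessment should be repeated". Appendix A item 12 has the same condition and also holds first: the patient "should stop study medication temporarily until normalization of renal function or confirmation of renal impairment diagnosis".

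**Section 7.7.** This section words the rule differently: "Patients with a confirmed CrCl <60 mL/min/1.73 m² should stop study medication temporarily". The assessment is then repeated and, if the impairment is confirmed, "the patient should stop study medication permanently (see Section 3.6", with Section 3.6 cited as its source. It does not require chronic renal disease.

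**The concern.** Two things are at odds in the current text, not merely in the amendment log.

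First, the unit. A Cockcroft-Gault value in mL/min decides entry. A value per 1.73 m² decides stopping. The protocol names no other equation and says nothing about body surface area or how to index to it. Either the suffix is a slip carried through four places, or a conversion step is missing. A site cannot tell which, and neither can whoever sets up the laboratory report.

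Second, the trigger for the hold. Sections 3.6 and 7.7 cannot both be followed as written. They differ on whether one low value is enough to hold the drug and on whether chronic renal disease must be present.

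The renal stopping rule was added by Amendment 04 to avoid higher laquinimod exposure, after the cardiovascular events at higher doses in the MS trials. What is at stake is whether a patient-level dosing decision is made the same way at every site. No efficacy comparison depends on it.

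**Working it through.** **Unit.** The protocol gives no figure to reproduce beyond the number 60, which appears in both limits.

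Inputs: entry limit 60 mL/min (Section 4.2, exclusion h); stopping limit 60 mL/min/1.73 m² (Section 3.6, footnote t, Section 7.7, Appendix A item 12). Body surface area (BSA) is assumed, because the protocol gives none.

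Indexed clearance = clearance × 1.73 / BSA, so the stopping limit in plain mL/min is 60 × BSA / 1.73:

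| BSA (assumed), m² | Stop, mL/min | Difference from entry limit |
|---|---|---|
| 1.5 | 60 × 1.5 / 1.73 = 52.0 | −8.0 |
| 1.6 | 60 × 1.6 / 1.73 = 55.5 | −4.5 |
| 1.73 | 60.0 | 0 |
| 2.0 | 60 × 2.0 / 1.73 = 69.4 | +9.4 |
| 2.2 | 60 × 2.2 / 1.73 = 76.3 | +16.3 |

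The limits coincide only at 1.73 m². They drift apart by 6 / 1.73 = 3.5 mL/min for each 0.1 m².

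Two invented patients show both directions (BSA by Mosteller; serum creatinine read as part of the denominator of the printed formula):

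- Man, 50 years, 180 cm, 85 kg, creatinine 1.6 mg/dL. Cockcroft-Gault: 90 × 85 / (72 × 1.6) = 66.4 mL/min, so he passes criterion h. BSA = √(180 × 85 / 3600) = 2.06 m². Indexed: 66.4 × 1.73 / 2.06 = 55.7 (from unrounded values), already under the stopping limit on the same blood sample.
- Woman, 50 years, 155 cm, 50 kg, creatinine 0.95 mg/dL. Cockcroft-Gault: 90 × 50 × 0.85 / (72 × 0.95) = 55.9 mL/min, so she is excluded. BSA = √(155 × 50 / 3600) = 1.47 m². Indexed: 65.9, above the stopping limit.

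If the suffix is a slip, none of this arises and the gap is zero.

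**Trigger and order.** Set side by side and read literally:

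| Patient | Section 3.6, footnote t, Appendix A item 12 | Section 7.7 |
|---|---|---|
| Chronic renal disease, one low value | Hold now, then repeat or confirm | No hold until the value is confirmed |
| Chronic renal disease, low value confirmed | Permanent stop | Temporary hold, then a further repeat before permanent stop |
| No chronic renal disease, low value confirmed | Nothing required | Temporary hold, then permanent stop if confirmed again |

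For patients judged to have chronic renal disease, Section 7.7 therefore acts one test later. For all others it is the only text that acts at all. The permanent-stop wording in Appendix A item 12 is not a further conflict: it uses the same limit of 60, although it does not name a repeat test.

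**The case against.** The strongest reply is that a site has a workable rule. Section 3.6, footnote t and Appendix A item 12 agree with each other. Section 3.6 sends the reader to Appendix A for detail, and Section 7.7 sends the reader back to Section 3.6 and describes its purpose as monitoring chronic renal function. On that view one stray word in Section 7.7 departs from a clear majority. The unit may also be a slip that the central laboratory's report settles in practice. This stands as a reason to think that Section 7.7 is the text in error and that the repair is small. It does not remove the contradiction: the cross-reference leads to different wording, and the protocol does not state the laboratory's equation or unit.

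Three stronger readings are tempting but not supported.

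- **That Section 7.7 leaves patients on drug for 9 to 13 more weeks.** Those are the gaps between in-clinic visits from Week 4 on, but no text says that confirmation must wait for one. Table 3 and Section 3.11.5 allow the calculation at an unscheduled visit, which could take days. The range also omits the 4 weeks from baseline to the Week 4 visit.
- **That the defect exposes a patient on 1.0 mg/day to about 1.4 mg/day.** The 1.4-fold increase in Section 1.3.2.1 is for moderate renal impairment as a group. It explains why a renal rule exists. It does not measure the effect of a different unit or one extra test, and a patient just under 60 would probably have a smaller increase.
- **That Section 7.7 is simply the laxer rule.** It is later for patients with chronic renal disease and broader for everyone else.

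**Conclusion.** The protocol is wrong as written on both counts. The entry and stopping limits are in different units with no conversion, and Section 7.7 contradicts three other places on when the drug is held and for whom.

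The size of the unit gap is conditional. It runs from 8.0 mL/min below the entry limit at 1.5 m² to 9.4 above it at 2.0 m² if indexing was meant and those assumed body sizes apply, and it is zero if the suffix is a slip. The trigger conflict needs no such assumption, but no duration or exposure can be attached to it from the text.

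Few patients are likely to be affected: the age range is 21 to 55, renal disease is an excluded condition under exclusion i.6, and an abnormal screening laboratory result can exclude under criterion j. Sample size, power and type I error are untouched. The point merits correction because it is a safety dosing rule and the repair is cheap.

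**What to change.** - **Unit.** Use one equation and one unit for entry and stopping. Cockcroft-Gault in mL/min matches the only equation named; this means deleting the per-1.73 m² suffix in Section 3.6, Table 3 footnote t, Section 7.7 and Appendix A item 12. If indexing was intended, keep it, state the conversion, and put the entry limit on the same scale. Deleting the suffix would then loosen the stop for patients above 1.73 m² (from 69.4 to 60 mL/min at 2.0 m²). Height at screening and weight at each in-clinic visit are already collected, so either choice is feasible.
- **Laboratory.** Check that the central laboratory's report uses the chosen equation and unit.
- **Section 7.7.** Delete the word *confirmed* from the hold sentence and give the section the same trigger as Section 3.6, so that every section follows hold, repeat, then stop. A time window for the repeat would help, but is not needed to remove the contradiction.

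The choice of limit, unit and trigger belongs to the sponsor and the DSMB. The cost is protocol wording in four places (plus exclusion h and its synopsis copy if indexing is kept) and one check with the laboratory. No new data are needed.
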